8.15 VISIT 7 (LAST DAY OF WEEK 54 ±7 DAYS)

- Verify compliance.
- Measure vital signs.
- Perform physical examination.
- Measure body weight and height for the BMI and Z-score calculations.
- Record AEs.
- Fill out TESS ([Appendix 5](#); to be completed by the Investigator with the parent/caregiver's input).
- Fill out CSDI ([Appendix 6](#); to be completed by the site coordinators/Investigator with the parent/caregiver's input).
- Fill out ESS ([Appendix 7](#); to be completed by the site coordinators/Investigator with the parent/caregiver's input. Note: The ESS is to assess sleepiness of the parent/caregiver and NOT the child.).
- Fill out WHO-5 questionnaire ([Appendix 9](#); to be completed by the site coordinators/Investigator with the parent/caregiver's input. Note: The WHO-5 is to assess the quality of sleep of the parent/caregiver and NOT the child.).
- Fill out PSQI questionnaire ([Appendix 8](#); to be completed by the site coordinators/Investigator with the parent/caregiver's input. Note: The PSQI is to assess the well-being of the parent/caregiver and NOT the child.).
- Collect and dispense Epilepsy Seizures Diaries for patients diagnosed with epilepsy ([Appendix 10](#); to be completed by the parent/caregiver after each seizure).
- Collect the Sleep and Nap Diary ([Appendix 1](#); to be completed by the parent/caregiver during the 14 nights before Visit 8). If the Sleep and Nap Diaries were completed on a paper version, then the diary data is to be entered into the eCRF.
- Explain and dispense study drug (IMP Handling Guidelines).
- The visit should be carried out within ±7 days.

8.16 PRE-VISIT 8

Make follow-up phone call once a month until Visit 8.

8.17 VISIT 8 (LAST DAY OF WEEK 106 ±7 DAYS)

- Verify compliance.

- Measure vital signs.
- Perform physical examination.
- Measure body weight and height for the BMI and Z-score calculations.
- Record AEs.
- Assess pubertal status using the Tanner scale (The Tanner scale will be used to assess and stage physical development in children ≥ 8 years of age. For children ≤ 5 years of age, only height and head circumference will be used to stage children development. Between the age of 5 and 8 the children's physical development will be determined using the BMI.)
- Fill out TESS ([Appendix 5](#); to be completed by the site coordinators/Investigator with the parent/caregiver's input).
- Fill out CSDI ([Appendix 6](#); to be completed by the site coordinators/Investigator with the parent/caregiver's input).
- Fill out ESS ([Appendix 7](#); to be completed by the site coordinators/Investigator with the parent/caregiver's input. Note: The ESS is to assess sleepiness of the parent/caregiver and NOT the child.).
- Fill out WHO-5 questionnaire ([Appendix 9](#); to be completed by the site coordinators/Investigator with the parent/caregiver's input. Note: The WHO-5 is to assess the quality of sleep of the parent/caregiver and NOT the child.).
- Fill out PSQI questionnaire ([Appendix 8](#); to be completed by the site coordinators/Investigator with the parent/caregiver's input. Note: The PSQI is to assess the well-being of the parent/caregiver and NOT the child.).
- Collect and dispense Epilepsy Seizures Diaries for patients diagnosed with epilepsy ([Appendix 10](#); to be completed by the parent/caregiver after each seizure).
- Explain and dispense study medication (placebo run-out) (IMP Handling Guidelines).
- The visit should be carried out within ± 7 days.

8.18 PRE-END OF STUDY VISIT

Make follow-up phone call 1 week before the end of study visit to ensure that patients are taking study treatment and to schedule an end of study visit.

8.20 UNSCHEDULED VISIT(S)

At any point during the study, the Investigator could call the patient in for an unscheduled visit if the Investigator was concerned about safety issues; the unscheduled visit page in the eCRF should be completed if such a visit takes place.

9 EFFICACY ASSESSMENTS

Primary Efficacy Endpoint

The primary efficacy endpoint is TST time as assessed by a Sleep and Nap Diary after the 13-week, double-blind treatment period.

Secondary Efficacy Endpoints

- Sleep latency as assessed by a Sleep and Nap Diary after 13 weeks (Week 15) of double-blind treatment
- Duration of wake after sleep onset period from the Sleep and Nap Diary after 13 weeks (Week 15) of double-blind treatment
- Number of awakenings from the Sleep and Nap Diary after 13 weeks (Week 15) of double-blind treatment
- Longest sleep period from the Sleep and Nap Diary after 13 weeks (Week 15) of double-blind treatment
- Social functioning at home, in school, and in community settings as assessed by the CGAS after 13 weeks (Week 15) of double-blind treatment.
- Behavior at home and in school as assessed by the SDQ after 13 weeks (Week 15) of double-blind treatment
- Number of dropouts during the 13 weeks (Week 15) of double-blind treatment period.
- Assessment of sleep parameters by actigraphy after 13 weeks (Week 15) of double-blind treatment

Exploratory Efficacy Endpoints

- Sleep variables as assessed by the Sleep and Nap Diary at baseline (Week 2), after 3 weeks of double-blind treatment (Week 5), and after 13, 26, and 39 weeks of open-label treatment (Weeks 28, 41, and 54)
- Sleep disturbance as assessed by the CSDI score at baseline after 3 and 13 weeks of double-blind treatment (Weeks 5 and 15, respectively), after 13, 26, 39, and 91 weeks of open-label treatment (Weeks 28, 41, 54, and 106, respectively), and at the end of study visit (Week 108)
- Social functioning at home, in school, and in community settings as assessed by the CGAS after 13 weeks (Week 28) of open-label treatment
- Behavior at home and in school as assessed by the SDQ after 13 weeks (Week 28) of open-label treatment
- Caregiver's daytime sleepiness (i.e., NOT the child's) during the study as assessed by the ESS (Weeks 0, 2, 5, 15, 28, 41, 54, 106, and 108)

- Caregiver's well-being (i.e., NOT the child's) during the study as assessed by the WHO-5 questionnaire (Weeks 0, 2, 5, 15, 28, 41, 54, 106, and 108)
- Caregiver's quality of sleep at night (i.e., NOT the child's) during the study as assessed by the PSQI questionnaire (Weeks 0, 2, 5, 15, 28, 41, 54, 106, and 108)

10 CLINICAL PHARMACOLOGY ASSESSMENTS

10.1 PHARMACOKINETIC (PK) ASSESSMENTS

Not applicable.

10.2 PHARMACODYNAMIC (PD) ASSESSMENTS

Not applicable.

10.3 BIOMARKER AND EXPLORATORY ASSESSMENTS

Not applicable.

11 SAFETY ASSESSMENTS

11.1 ADVERSE EVENTS

It is the responsibility of the Investigator to document all AEs that occur during the study. Adverse events should be elicited using the TESS ([Appendix 5](#)).

11.1.1 Definition of an Adverse Event

An AE is defined as any untoward medical occurrence in a patient or clinical investigation patient who is administered a pharmaceutical product during participation in an investigational study, which may or may not have a causal relationship with this treatment.

An AE can therefore be any unfavorable and unintended sign (e.g., an abnormal laboratory finding or physical examination), symptom, or disease temporally associated with the use of a medicinal product, whether or not considered related to the medicinal product.

An AE includes any noxious, pathological or unintended change in anatomical, physiological or metabolic functions as indicated by physical signs, symptoms and/or laboratory changes whether associated with the study drug and whether or not considered drug related. This includes an exacerbation of pre-existing conditions or events, intercurrent illnesses, drug interaction or the significant worsening of the indication under investigation that is not recorded elsewhere in the eCRF under specific efficacy assessments. Anticipated day-to-day fluctuations of pre-existing conditions, including the disease under study, which do not represent a clinically significant exacerbation or worsening, need not be considered AEs.

Patient entry into the study is defined as the time at which informed consent is obtained (this must be before any protocol-specific diagnostic procedures or interventions). All AEs on this study subsequent to Visit 1 must be reported regardless of whether or not they are considered related to study drug. Any

AEs experienced subsequent to signing of the informed consent/assent will be recorded as a medical history item.

At Visit 1, the TESS questionnaire ([Appendix 5](#)) is completed and the information is used to assess medical history. All symptoms that are score of 1 or more should be recorded in the medical history as it will serve us throughout the study as a baseline to see if a symptom was worsen or not. At Visit 2 and all subsequent visits thereafter, the TESS questionnaire is used to report all treatment-emergent signs and symptoms that may have occurred since Visit 1. As instructed in [Appendix 5](#), a given sign and symptom is to be reported as a corresponding AE if a score of 1 or above is selected, and if the sign or symptom is a new symptom or if there is an increase in severity of an existing symptom from the first visit (i.e., Visit 1). If a specific symptom has the same score or lower from Visit 1 AEs should not be reported.

Adverse events are also to be reported on the appropriate page of the patient's eCRF.

11.1.2 Assessment of Severity

Each AE will be assigned a category as follows:

- Mild:* Not sufficiently intense to result in discontinuation of the study drug. Symptomatic treatment may have been given.
- Moderate:* Sufficiently intense to result in discontinuation of the study drug. Symptomatic treatment may have been given.
- Severe:* More intense than moderate; moreover the AE interferes significantly with ability to do work or usual activity.

A change in the severity of an AE will require it to be recorded as a separate event.

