12 DATA MANAGEMENT AND STATISTICAL ANALYSIS

12.1 DATA MANAGEMENT

An eCRF will be used for the current study and a data management plan will be prepared.

The site will be supplied with the following data collection tools: a web browser address for an Electronic Data Capture (EDC) system database that has been fully validated and conforms to 21 CFR Part 11 and the Guidance for Industry on Computerized Systems Used in Clinical Trials requirements. The EDC system database will be maintained by Datatrial.

Trained site staff will enter the data required by the protocol into the eCRFs from source documents (e.g., medical records and study-specific data capture forms as needed) into the EDC system. All information on the eCRFs must be traceable to these source documents. Data recorded directly on the eCRFs will be defined before study start. The eCRFs will be completed for all patients randomized to study treatment. The eCRFs for patients who are randomized but not treated will be completed with all data collected at the time of patient study discontinuation. Screen failures should also be entered into the eCRF. Clinical Research Associates will review the eCRFs entered by investigational staff for completeness and accuracy.

Automatic validation programs check for data discrepancies in the eCRFs resulting in electronic queries generated for resolution by the investigational site. Designated site staff is required to respond to queries and make any necessary changes to the data. After database lock, the Investigator will receive the patient data on a CD for archiving at the investigational site.

All treatment-emergent AEs (events occurring from the first dose of study medication through the last study evaluation) will be recorded in the EDC system. AEs will be coded using the MedDRA dictionary (version 16.1) and concomitant medications will be coded using a standard dictionary (e.g., WHODrug, dated March 2013).

The process of randomization and allocating randomized treatments using the eCRF is described in the eCRF completion guidelines and the IMP Handling Guidelines.

When the database has been declared to be complete and accurate, the database will be locked. Any changes to the database after that time can only be made by written agreement between Neurim and the PRA Health Sciences project team.

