9.4 Missing Dates

For partial date of births, where the day and month are missing, they will be replaced with 30/06.

The following will be applied to start and end dates for baseline histories, concomitant medications and adverse events where required for calculation of durations and assignment to phases. No imputed values will appear in the listings.

- If the day is unknown and the month and the year are known, it will be replaced by 01 in the case of a start date or by the last day of the month in the case of an end date.

- If the day and the month are unknown, they will be replaced by 01/01 in the case of a start date or 31/12 in the case of an end date.
- If the day, the month and the year are unknown, the date will be considered as missing.

For start and end dates of AEs, there is an exception from the above mentioned rules:

- If the day is unknown and the month and the year are the same as the first treatment intake known, it will be replaced by the date of first treatment intake.
- If the day and the month are unknown and the year is the same as the first treatment intake known, it will be replaced by the date of first treatment intake.

10 Subject Disposition, and Demographic and Baseline Characteristics

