12.3 Adverse Events

AEs will be coded according to MedDRA® version 18.0 or higher.

An overall AE summary will be presented for the following pre-defined subsets of events:

- Any TEAEs
- Any TEAEs considered related to treatment
- Any TEAEs leading to study drug discontinuation
- Any SAEs
- Any deaths
- Any SAEs considered related to treatment
- Any SAEs leading to study drug discontinuation

Listings by subject will be presented for the following subsets:

- Any TEAEs

- Any SAEs

All TEAEs will be summarized and grouped by MedDRA® System Organ Class (SOC) and specific AE preferred term (PT). Results will be displayed in order of decreasing frequency by SOC and PT.

Summaries will also be produced of SAEs, treatment related AEs and TEAEs leading to study drug discontinuation by SOC and PT terms. In addition, a summary will be provided by severity (mild, moderate, severe).

For all summary tables, both number of events and number of subjects will be tabulated. For subjects, percentages will be calculated from the total number of subjects per treatment group. Related to treatment is defined as any adverse events considered either “possibly”, “probably” or “definitely” related to study drug.

Tables will be presented for the double blind and open-label phases separately.

In addition a cumulative summary will also be presented for all subjects on active treatment for all TEAEs, SAEs and TESAEs leading to discontinuation of study drug grouped by SOC and PT terms occurring in either the double blind or open-label phase.

For the purposes of the interim analysis reporting, an AE cut-off point will be defined as any AE starting on or before Visit 5.

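### Each severity change of an AE becomes a separate event, and the SAP has no rule that joins records of one episode, so event counts, severity rows and open-label entries are overstated

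*Protocol*

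**What the plan says.** **Recording.** Protocol 11.1.2 states: "A change in the severity of an AE will require it to be recorded as a separate event". No direction of change is given. For symptoms elicited by TESS, Protocol 11.1.1 compares each score with Visit 1, not with the previous visit: "If a specific symptom has the same score or lower from Visit 1 AEs should not be reported". SAP 12.2 repeats this. An AE that eases but stays above its Visit 1 score therefore remains reportable.

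**Treatment-emergent.** Protocol 12.1 defines these AEs by date only: "events occurring from the first dose of study medication through the last study evaluation". SAP 12.3 adds no condition that the AE be new or worse.

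**Counting.** SAP 12.3: "For all summary tables, both number of events and number of subjects will be tabulated". Percentages are based on children. A summary by severity is also planned (Tables 14.3.2.10 and 14.3.2.11).

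**Phases.** SAP 12.3: "Tables will be presented for the double blind and open-label phases separately". It adds cumulative tables on active treatment (Tables 14.3.2.14 to 14.3.2.16). Under SAP 9.2, open-label tables show the original arm and an All Circadin column. No rule says which phase an AE belongs to. SAP 9.4 imputes dates for "concomitant medications and adverse events where required for calculation of durations and assignment to phases", and the reporting cut-off is by start date: "an AE cut-off point will be defined as any AE starting on or before Visit 5".

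**The concern.** The recording rule splits one episode into several events, and nothing in the analysis plan puts them together again. An event count then partly measures how much an AE fluctuates rather than how often AEs occur. In the severity tables one episode can fill several rows.

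The more serious effect is at Visit 4, when placebo children move to open-label Circadin. If an AE that began on placebo eases a few weeks later, the easing creates a record with an open-label start date. A sign of recovery is then displayed as a Circadin AE. AEs are a secondary endpoint (SAP 4.2), and these tables feed the Week 28 report that is submitted for approval (SAP 1 and 13).

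**Working it through.** The plan states no figure on this point, so there is none to reproduce.

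**1. Records per episode.** Under Protocol 11.1.2, records = 1 + number of severity changes while the AE lasts. Mild-moderate-mild gives 1 + 2 = 3. Mild-moderate-severe-moderate-mild gives 1 + 4 = 5. The double-blind phase is Weeks 3 to 15, and the first open-label phase is Weeks 16 to 28 (Protocol Table 5-1). The table shows double-blind + open-label records, with each record placed by its start date.

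| Course | Visit 1 score | As written | New record only on worsening | One per episode |
|---|---|---|---|---|
| Mild, moderate, mild, all double-blind | 0 | 3 + 0 | 2 + 0 | 1 + 0 |
| Mild up to severe and back to mild, all double-blind | 0 | 5 + 0 | 3 + 0 | 1 + 0 |
| Moderate Week 14, mild Week 17 | 0 | 1 + 1 | 1 + 0 | 1 + 0 |
| Severe Week 14, moderate Week 17, mild Week 20 | 0 | 1 + 2 | 1 + 0 | 1 + 0 |
| Severe Week 14, moderate Week 17, mild Week 20 | mild | 1 + 1 | 1 + 0 | 1 + 0 |
| Moderate Week 14, mild Week 17 | mild | 1 + 0 | 1 + 0 | 1 + 0 |

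The last row marks a limit: a return to the Visit 1 level makes no new record.

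**2. Severity rows.** In the first course the child has two mild records and one moderate record. Without a maximum-severity rule, one child counts once in each of two rows.

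**3. Which phase.** The record that starts in Week 17 falls in the open-label tables under a start-date rule. It does so too under a starts-or-is-ongoing rule, such as SAP 10.6 uses for concomitant medication. For a placebo child it then adds an event and a child under All Circadin and in the cumulative active-treatment tables.

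**4. Size under assumed rates.** The documents give no rates. Assumptions:
- 13 double-blind and 13 open-label weeks, with no drug effect.
- Weekly onset 2%, weekly resolution 5% to 20%.
- Weekly chance of a one-grade step 5% to 20%, up or down equally, with no step below mild or above severe.
- Every weekly change is captured.

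Simulation gives:
- Recorded events divided by episodes: about 1.1 to 2.1. Hand check of the lower end: at 20% resolution an episode lasts on average 0.8/0.2 = 4 further weeks. A mild AE can only step up, so it has 4 × 0.05 × 0.5 = 0.10 changes, a ratio of about 1.10.
- Children with any open-label record, minus children with a new onset or an upward step: close to 0 up to about 1.2 points if every AE starts mild, and up to about 2.9 points if onset grades are spread evenly. For scale, 2% a week over 13 weeks allows at most 1 − 0.98^13 = 23.1% of children with a new onset.

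**The case against.** Several counter-arguments are sound.

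- **Percentages of children.** A reader might infer that these are inflated too. Within one phase they are not: repeat records do not change whether a child has had a given preferred term.
- **Bias between arms.** A reader might infer bias in the randomised comparison. The rule applies equally to both arms, and nothing in the documents shows a difference.
- **Grade definitions.** Protocol 11.1.2 defines moderate as intense enough to result in discontinuation of study drug, so a moderate AE that eases on continued treatment sits badly with the definition. It is still possible, because withdrawal for an AE is discretionary (Protocol 11.3) and the TESS grades carry no such condition. If every child left at moderate, the open-label excess would be zero, since a carried-over AE would be mild and could only resolve or worsen. The event ratio would be about 1.1 to 1.5.
- **Phase rule.** The open-label effect is inferred, because the SAP states no AE phase rule. Under a starts-or-is-ongoing rule the AE would enter the open-label tables even without the split. That is a reason to state the rule, not a defence of the plan.
- **Run-in symptoms.** A reader might infer that any run-in symptom that eases after randomisation becomes a double-blind AE. It does not if it was at the same or a higher score at Visit 1.
- **Capture.** TESS is given only at visits, so many weekly changes would go unrecorded. Record linking in the eCRF completion guidelines, which are not available here, cannot be excluded.
- **Comparator.** Setting recorded incidence against new onsets alone gives a larger gap, but most of that gap is genuine worsening, which should be counted.

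None of this supplies a linking rule or a maximum-severity rule.

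**Conclusion.** The concern holds in a limited form. A stated recording rule, followed literally, overstates event counts and puts one child in several severity rows. It can also show an AE that began on placebo and is easing as an open-label Circadin AE, provided the AE stays above its Visit 1 level. Percentages of children per preferred term within a phase and the primary efficacy analysis are untouched.

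The counts worked by hand (3 or 5 events for one episode) follow from the text. The ranges of about 1.1 to 2.1 for events and about 0 to 3 percentage points for open-label child incidence rest wholly on assumed rates. They are upper-end illustrations, because TESS is given only at visits and a moderate AE may end treatment. The second range is measured against a count that accepts any upward step. The rule under the fix is stricter, so under the same assumptions it would remove somewhat more.

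The plan should be changed: the safety tables support a submission, and the correction needs only a derivation.

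**What to change.** Add to SAP 12.3, before unblinding:

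- (a) Contiguous records of the same preferred term in one child that differ only in severity are one event, with the first start date, the last stop date and the maximum severity within the phase. Define contiguous by dates.
- (b) Each event belongs to the phase of its first onset. It counts again in a later phase only if its severity there exceeds the maximum reached in the earlier phase. The same rule decides whether an event that began on placebo enters the cumulative active-treatment tables.
- (c) In the severity tables, each child counts once per preferred term, at maximum severity.
- (d) All raw records stay in Listing 16.2.7.2.

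The mild, moderate and severe definitions in Protocol 11.1.2 and the TESS grades in Protocol Appendix 5 must also be reconciled, so that one scale underlies the tables.

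The SAP change costs one paragraph and a short derivation step. It needs no new data and no change at the sites.
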